3.2 Informed Consent, Participant Surveys, and Educational Intervention

As patients wait to have the mammogram, they will be screened for eligibility. Following completion of the mammogram, patients will return to the changing room and put on their clothing. After exiting the changing room in the Lynn Sage Comprehensive Breast Center of Northwestern Medicine/Prentice Women's Hospital and as they are preparing to leave, a research assistant (RA) will interview potential participants to acquire a randomly selected convenience sample of eligible participants (n=800). Participants will be invited to complete a survey that will assess knowledge of melanoma and the risk of developing a melanoma. They will be provided with a consent form and the research study will be discussed, questions will be invited and then they will be asked to sign a consent form and to fill out a registration form containing contact information. (see attached)

The complete survey includes general demographic items such as age, education, household income, race and ethnicity. The survey questions are as follows:

1. During your visit for mammography, did you notice any information about checking your skin for melanoma?

Yes No

2. Did you think this applied to you?

Yes No

3. If no, why not? (open ended)

4. If yes, why? (open ended)

5. Did you check your skin? (If no, please proceed to question #7)

Yes No

6. If yes, did you notice any concerning moles?

Yes No

7. If no, will you consider checking your skin in the future?

Yes No

8. If you found any concerning moles, did you make an appointment to see a dermatologist?

Yes No

The RA will record the responses.

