3.3 Research procedures and activities

Follow-Up

1 week after the mammogram, RA will contact participants in group 1 via their preferred method to remind them to perform SSE and schedule a dermatologist appointment if they find a concerning mole. (see attached telephone script)

1 month after the mammogram, the RA will call participants in group 1 and administer a survey to see if they checked their skin and/or made an appointment with a dermatologist.

Effect of SSE education delivered during the mammography experience.

(see attached telephone script) An anonymous REDCap survey may be used in place of the telephone call, depending on participant's preferred method of contact preference.

The survey questions are as follows:

1. Did you read the brochure?
 Yes No
2. Did you check your skin? (If no, please proceed to question #4)
 Yes No
3. If yes, did you notice any concerning moles?
 Yes No
4. If no, will you consider checking your skin in the future?
 Yes No
5. If you found any concerning moles, did you make an appointment to see a dermatologist?
 Yes No

If no, do you intend to do so in the near future?

6. Did you share the brochure with anyone else?
 Yes No
7. If yes, who did you share it with:
 - a) A relative: son, daughter, father, mother, sister, brother
 - b) A friend : woman, man
 - c) Someone I work with: woman, man

REDCap Survey

3 months after the mammogram, an anonymous REDCap survey will be emailed to each woman enrolled in both groups. If participants do not complete the REDCap survey in 2 weeks, they will be called and surveyed via telephone. The following items with relevance to the research:

1. Do you have a history of sunburn? Yes/No
2. Do you have a history of more than 10 indoor tanning sessions? Yes/No
3. Do you have a personal or family history of melanoma? Yes/No
4. Have you ever performed a skin self-examination prior to your most recent mammogram? Yes/No

Effect of SSE education delivered during the mammography experience.

5. Did you perform a skin self-examination after your most recent mammogram?
Yes/No
If no, then go to item 8.
6. Did you find a concerning mole? Yes/No
7. If you found a concerning mole, did you make an appointment to see a dermatologist? Yes/No
8. If you did not perform a skin self-examination, did you still make a follow-up appointment to see a dermatologist for a skin examination? Yes/No
9. Have you had an appointment with a dermatologist yet? Yes/No

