10.0 Risks to Participants

10.1. The potential risks to participants are expected to be minimal, if they occur. Subjects will be participating in an educational intervention that may enhance their awareness of their risk of developing skin cancer. All study participants will be provided with an email address

Effect of SSE education delivered during the mammography experience.

and phone number to contact study staff in the event they have concerns. If a subject becomes concerned that they have a suspicious lesion, the control subject will be instructed to make an appointment with their own dermatologist for an examination. The research assistant will communicate other concerns to the PI. In such circumstances, [name] will consult with the patient's own dermatologist and an appropriate referral will be made.

Because of the potential for the educational intervention to help the subject identify melanoma at a stage of development with the best prognosis, we feel that the potential benefits, in reduced morbidity and mortality, to the subject outweigh the risk of potential enhanced anxiety in discovering a suspicious mole. Should subjects report high levels of anxiety a referral for psychological support will be made.

10.2. We do not believe that subjects in this study will be exposed to any risk of physical or psychological harm as a result of either the intervention or research processes. Our measures do not assess individuals at risk of immediately harming themselves (e.g. suicide); therefore we will not have to screen the data to potentially intervene with individuals who may be a risk to themselves.

10.3. N/A. There are no anticipated risks to others who are not participants.

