14.0 Data Analysis

14.1. This convenience sample of women undergoing screening mammography will all receive education either as a brochure and a 1-week reminder or as only the brochure. Demographic characteristics of the two groups will be examined using means and standard deviations (age) and counts and percentages for all categorical variables. Primary outcomes of SSE performance, biopsy, and diagnoses will be compared using Chi-square tests of association or Fisher's exact tests where sample sizes were restrictive. Due to the skewed nature of the anxiety scale, a Wilcoxon rank sum test will be used to compare anxiety, the secondary outcome, in the two groups. Descriptive statistics will be performed for the tertiary outcome of dissemination.

15.0 Confidentiality and Data Management:

1. There are no biological specimens. All of the following data is collected in person consent and responses to structured interviews and focus groups.
2. Our systems are guarded against outside entry by Northwestern's own firewall supporting 128-bit encryption. This level of encryption provides the highest level of protection against hackers, computer break-ins, etc. All data is deidentified. Experienced research assistants will be employed and will receive training that includes emphasis upon the importance of confidentiality of information, and all personnel on the project will complete the required NIH training in the protection of human research participants.
3. Data will be retained in separate locked file cabinets and on computers with restricted and password protected access, without links to the master code list. All data based on the research will be reported in aggregate form. No individual respondents will be identified. Electronic data will be maintained in a study specific database on the server of the Department of Dermatology at the Feinberg School of Medicine. Paper-based files will be kept in a locked cabinet in a locked room within the Northwestern University Department of Dermatology research offices. Identifiable data will be kept separate from the case report forms and source documents. Data gathered as a result of this study are available to inspection on request by Food and Drug Administration or other government regulatory agency auditors, and the Northwestern University Institutional Review Board (IRB).

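### Anxiety is the secondary outcome with its own test, but the plan gives no scale, scoring or time point, and no printed survey item measures it

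*Combined protocol and SAP*

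**What the plan says.** Section 14.0 Data Analysis (14.1) sets three tiers of outcome. The primary outcomes are performance of skin self-examination (SSE), biopsy and diagnoses, compared by chi-square or Fisher's exact test. For the second tier, "a Wilcoxon rank sum test will be used to compare anxiety, the secondary outcome, in the two groups", and the reason given for a rank test is "Due to the skewed nature of the anxiety scale". The third tier is dissemination, which is only described.

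The data sources printed in the protocol are these:

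- **List under 3.2 Informed Consent, Participant Surveys, and Educational Intervention.** The stated content is "Participants will be invited to complete a survey that will assess knowledge of melanoma and the risk of developing a melanoma", and "The complete survey includes general demographic items such as age, education, household income, race and ethnicity". Eight questions follow.
- **1-month survey under 3.3 Research procedures and activities.** The research assistant is to "administer a survey to see if they checked their skin and/or made an appointment with a dermatologist". Seven questions follow.
- **3-month REDCap survey, same section.** The list is introduced by "The following items with relevance to the research" and opens with "Do you have a history of sunburn? Yes/No". It has eleven numbered items.
- **Medical record review.** This covers the dermatologist's findings and the pathology of biopsied moles.

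Elsewhere, anxiety appears only as a possible risk. Section 10.0 says "Should subjects report high levels of anxiety a referral for psychological support will be made", section 11.0 repeats the promise, and section 15.1 gives women a contact to use if they become anxious or worried.

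**The concern.** A named outcome with a named test needs a measurement behind it. Here the analysis section relies on a scale, and even describes the shape of its distribution, while the data-collection sections print questions in which no such scale appears. A statistician working from this plan would not know what variable to analyse, how it is scored or when it is measured.

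What is at stake is the only secondary outcome. Group 1 receives a reminder one week after the mammogram and Group 2 does not, so whether the added contact raises anxiety is a fair comparative question. Sections 10.0 and 11.0 also weigh possible anxiety against expected benefit. Scores that are not collected during follow-up cannot be recovered afterwards, and a planned outcome without data leaves a gap in the report that has to be explained.

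**Working it through.** The plan gives no sample size, effect size or power figure for anxiety, so there is no figure to reproduce. The check is to read each printed source against what 14.1 requires: a score per woman, in both groups, on a scale with enough levels to be called skewed.

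**Step 1: count and classify the numbered items.**

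| Printed list | Numbered items | Yes/No | Open text | Category choice | On anxiety or worry |
|---|---|---|---|---|---|
| Under 3.2 Informed Consent | 8 | 6 | 2 | 0 | 0 |
| 1-month survey | 7 | 6 | 0 | 1 | 0 |
| 3-month survey | 11 | 11 | 0 | 0 | 0 |
| Total | 26 | 23 | 2 | 1 | 0 |

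Totals: 8 + 7 + 11 = 26 items, and 23 + 2 + 1 = 26 by type. The unnumbered follow-up question in the 1-month list (intention to make an appointment) and sub-items 10a and 10b of the 3-month list do not concern anxiety either. No printed item gives a graded score of the kind 14.1 describes.

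**Step 2: look for another source.**

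- Section 3.4 Measures lists risk factors, SSE, concerning moles, dermatology visits and biopsy, and not anxiety.
- The medical record review covers dermatology findings and pathology only.
- The two aims and the hypothesis in section 1.0 do not mention anxiety.
- Sections 10.0, 11.0 and 15.1 deal with women who report anxiety themselves. That gives no value for women who do not report, and no common scale, so it cannot feed a rank sum test.

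**Step 3: compare with the tertiary outcome.** Dissemination has a direct source: items 6 and 7 of the 1-month survey ask whether, and with whom, the brochure was shared. Of the two lower tiers, only anxiety lacks a printed source.

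**Step 4: see whether the surveys could carry a two-group comparison.** With 400 women per group and the anticipated 20% attrition, 400 × (1 − 0.20) = 320 per group would be followed up. The number of women is therefore no obstacle. Two other points are:

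- Section 3.1 Study Design has both groups surveyed at 1 month, whereas 3.3 Research procedures and activities describes that call for Group 1 only. The 3-month survey goes to both groups in both places.
- The REDCap surveys are described as anonymous. Section 15.0 says data carry a study number, and a yes to item 9 of the 3-month survey triggers a record check, so some link seems intended. How an anonymous answer is tied to a woman and her group is not stated.

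**The case against.** The strongest reply is that absence from the printed lists does not prove absence from the study. Section 14.1 speaks of the scale as something that exists. The protocol refers to attached telephone scripts and forms that are not in the text. The printed lists are visibly incomplete: the demographic items and the promised knowledge assessment under 3.2 Informed Consent are not among the eight questions there, and the lead-in to the 3-month list could be read as a selection.

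This reply stands in part. A reader might infer that the trial will hold no anxiety data on any of its 800 women. The documents do not support that, because an unprinted item cannot be excluded. They support the narrower statement about the printed instruments. The reply does not remove the gap: the other two lists are each introduced as the survey's questions, a secondary outcome is plainly relevant to the research, and a scale in an attachment would still leave 14.1 without a name, scoring rule or time point.

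Three smaller points also have weight:

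- The silence of 3.4 Measures is weak evidence alone, since that section omits dissemination too, which is collected.
- It is not certain that the list under 3.2 Informed Consent is asked at the visit. It asks about skin checks and appointments already made, and Study Design uses the term complete survey for the 3-month contact. The count of zero does not depend on this.
- Anxiety lies outside both stated aims, and the primary comparisons do not need it.

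**Conclusion.** The point holds as a mismatch between the analysis plan and the printed data collection: 0 of 26 numbered items measure anxiety, and its scale, scoring and timing are given nowhere. It rests on one assumption, that no anxiety item sits in an attachment that is not shown. If one does, the gap shrinks to the missing specification in 14.1.

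Two further inferences should be resisted. A reader might conclude that anxiety is the trial's only measure of harm. Biopsy is compared between groups under 14.1, and section 15.1 provides for adverse events and complaints. A reader might also conclude that the protocol presents anxiety as already evaluated. Sections 10.0 and 11.0 give only a prospective judgement about a potential risk.

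Because one secondary outcome is affected and the primary outcomes are not, the severity is moderate.

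**What to change.** Choose one of two courses.

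**Keep the outcome.** In 14.1, name the scale already presupposed there, or a short rating item in its place, with its scoring and one analysis time point. Add it to a survey given to both groups. The 3-month REDCap survey is simplest, because both sections agree on who receives it. If the 1-month contact is used, first reconcile 3.1 Study Design (both groups) with 3.3 Research procedures and activities (Group 1 only). In either case, state how each response is linked to study group when the survey is described as anonymous. If the scale is already in an attachment, citing it with its scoring and time point, and stating the link to study group, is enough.

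**Drop the outcome.** Remove anxiety and its Wilcoxon test from 14.1.

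The cost of keeping it is a slightly longer survey and a few sentences of text, with no added visits. The length of under 2 minutes is stated for the 3-month survey only; a single rating item should fit within it, while a longer scale may not. The cost of dropping it is losing the between-group comparison of anxiety.

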17.0 Qualifications to Conduct Research and Resources Available

17.1. All members of the research team have completed and maintained current Human Subjects Protection Training, such as CITI and the Department of Dermatology compliance modules. The PI has over 30 years of clinical research experience, including multiple NIH-funded studies and studies involving the educational training of physicians.

17.2 The PI's office is located within the clinical research office in the Clinical Research offices of the Department of Dermatology of Northwestern University. [name] skin cancer control group occupies 500 sq. ft. with 4 offices and a small conference room. All standard office equipment is available for use including PC, fax, color printer, locked filing cabinets, etc.

Northwestern provides web-based submission of IRB protocols and financial management.

There are no anticipated adverse consequences associated with the research. However, should a participant request medical or psychological resources, the PI and Co-Is are available for debriefing and will arrange referrals as necessary.

The PI will ensure that the RAs are thoroughly trained on the protocol, the research procedures, and their respective duties and functions. The RAs will be readily available to participants for questions and technical troubleshooting. The PI and RAs will personally

Effect of SSE education delivered during the mammography experience.

meet on a weekly basis to discuss study progress and review duties and functions as applicable. A continual, open dialogue among the PIs and RAs will be encouraged.

